8.2 Laboratory Evaluations

Schedules and volumes of blood to be collected for clinical laboratory tests and immunogenicity assays are specified in [Appendix 2](#).

8.2.1 Clinical Laboratory Evaluations

Clinical safety laboratory evaluations will be obtained at Screening and on Days 0, 7, 56, and 63. Specific tests to be performed are described below:

Screening Visit:

- Hematology: WBC with differential, HGB, platelets
- Chemistry: sodium, potassium, ALT, AST, total bilirubin, alkaline phosphatase, creatinine, random glucose.
- Serology tests: HIV 1/2 antibody, hepatitis B surface antigen (HBsAg), and hepatitis C virus (HCV) antibody.
- Urinalysis: will be performed by dipstick testing (includes protein and glucose).
- Pregnancy test: urine pregnancy test in females of childbearing potential or serum FSH for post-menopausal females.

Days 7 and 63:

- Hematology: WBC with differential, HGB, platelets.
- Chemistry: sodium, potassium, ALT, AST, total bilirubin, alkaline phosphatase, and creatinine.

Days 0 and 56:

- Pregnancy test: urine pregnancy tests on Days 0 and 56 in females of childbearing potential.

One or more of the laboratory parameters may be repeated at any time during the study as determined by the PI or licensed clinical study physician, if indicated by an AE. Screening laboratory values that are abnormal, but are considered abnormal due to an acute illness or process may be repeated once. A clinically significant abnormal value should be repeated within 10 days if possible and followed up as clinically relevant.

8.2.2 Special Assays or Procedures

Screening Visit:

- Prior exposure to TB antigens (prior infection with Mtb or vaccination with BCG) will be assessed using QuantiFERON®-TB Gold tests at the screening visit. Positive results will result in exclusion from the study and referral to medical treatment.

Days 0, 14, 56, 70, 84, 224:

- IgG antibody response in serum (secondary outcome measure)

- ID93-specific antibody responses will be measured by IgG binding to the ID93 protein using ELISA. Studies will be performed at IDRI.
- ELISpot and ICS assays in PBMC (secondary outcome measures)
 - T cell immune responses will be assessed by enumerating antigen-specific, cytokine-secreting T cells using IFN- γ enzyme-linked immunosorbent spot assays (ELISpot) and flow cytometry-based intracellular cytokine staining (ICS) from PBMC samples. Both assays will be performed at IDRI.

Days 0, 70, 224:

- IgA antibody response in mucosal secretions (exploratory outcome measure)
 - Antibody responses will be measured in nasal swab and tear specimens by IgA binding to the ID93 protein using ELISA. Assay will be performed by [name]'s laboratory at Saint Louis University.

Days 0, 70, 224:

- Mtb growth inhibition in whole blood (exploratory outcome measure)
 - Functionality of the immune response will be assessed by measuring the capacity of whole blood to inhibit the growth of mycobacteria. Assay will be performed by [name]'s laboratory at Saint Louis University.

Days 0, 7, 14, 63, 70, 224:

- Exploratory cellular immune responses (exploratory outcome measures)
 - PBMC samples will be used to quantitate the number of antibody-secreting cells in PBMC by short-culture B cell ELISpot, the number of antigen-specific memory B cells in PBMC by long-culture B cell ELISpot, and the frequencies of T follicular helper cells, memory B cells, and T cell homing markers in PBMC by immunophenotyping flow cytometry. Studies will be performed at IDRI.

8.2.3 Specimen Shipment

All participant samples (except for whole blood specimens) will be processed and stored through Study Day 224. Whole blood specimens are used fresh by the site and therefore not stored. Mucosal specimens will remain at the site for analysis (tears, nasal swabs). PBMC and serum specimens will be shipped to IDRI for analysis after the last Day 224 specimens are stored. PBMC and serum specimens from a single participant will be divided into separate boxes for storage and shipment. Shipment of PBMC and serum samples from the same individual and time point will take place on separate dates in case of specimen loss due to temperature excursions/deviation in cold chain.

9 ASSESSMENT OF SAFETY

9.1 Specification of Safety Parameters

Safety will be assessed by the frequency and severity of:

1. Serious adverse events occurring from the time of the first study injection through the entire study period.
2. Solicited adverse events – reactogenicity events occurring on the day of each study injection through 7 days after each study injection. This time period may be extended if a subject notes ongoing local or systemic reactogenicity on day 7 post study injection:
 - a) Injection site reactions including pain, induration (hardening/swelling), and erythema (redness).
 - b) Systemic reactions including headache, arthralgia (generalized joint pain), chills, loss of appetite, fever, fatigue, and myalgia (generalized muscle pain).
3. Unsolicited adverse events – non-serious adverse events occurring from the time of the first study injection through Day 84, including vital sign and safety laboratory abnormalities.
4. New-onset potential immune-mediated medical conditions (PIMMCs) occurring from the time of the first study injection through the entire study period.

9.2 Methods and Timing for Assessing, Recording, and Analyzing Safety Parameters

9.2.1 Adverse Events

Adverse Event: Adverse event means any untoward medical occurrence associated with the use of a drug in humans, whether or not considered drug or study injection related. An adverse event (also referred to as an adverse experience) can be any unfavorable and unintended sign (e.g., an abnormal laboratory finding), symptom, or disease temporally associated with the use of a drug, and does not imply any judgment about causality. An adverse event can arise with any use of the drug (e.g., off-label use, use in combination with another drug) and with any route of administration, formulation, or dose, including an overdose.

All conditions that exist prior to administration of the study injection (pre-existing conditions) will be recorded in the participant's medical history to establish baseline. Day-to-day fluctuations in pre-existing conditions that do not represent a clinically significant change in the participant's status will not necessarily be reported as adverse events.

Any adverse change from the participant's baseline condition (determined from screening evaluations conducted to confirm study eligibility) that occurs following the administration of the study injection will be considered an adverse event. This includes the occurrence of a new adverse event or the worsening of a baseline condition, whether or not considered related to the study injection. Intermittent conditions such as headaches may be present on Study Day 0, but may represent an adverse event if the frequency, intensity, or duration of the event is worse than usual following receipt of study injection. Adverse events include but are not limited to: adverse changes from baseline that represent increases in toxicity grade, adverse changes in the general condition of the participant, signs and symptoms noted by the participant, concomitant disease with onset or increased severity after study injection administration, and changes in laboratory safety parameters occurring after study injection administration.

A **suspected adverse reaction** is any adverse event for which there is a *reasonable possibility* that the study injection caused the event. Suspected adverse reactions are a subset of all adverse events. For example, headache or fever following study injection.

An **adverse reaction** is any adverse event *definitely* caused by the study injection. Adverse reactions are a subset of all suspected adverse reactions. For example, local site of injection erythema or pain at the site of injection.

Unexpected Adverse Event: An adverse event is considered "unexpected" if it is not listed in the Investigator's Brochure or is not listed at the specificity or severity that has been observed.

Serious Adverse Event: An adverse event is considered a *serious* adverse event (SAE) if, in the view of either the investigator or sponsor, it results in any of the following outcomes:

- death,
- a life-threatening adverse event,
- inpatient hospitalization or prolongation of existing hospitalization,
- persistent or significant disability/incapacity or substantial disruption of the ability to conduct normal life functions,
- a congenital anomaly/birth defect in the offspring of a study subject.

Important medical events that may not result in death, are not life-threatening, or do not require hospitalization may be considered an SAE when, based upon appropriate medical judgment, they may jeopardize the subject and may require medical or surgical intervention to prevent one of the outcomes listed in this definition. Examples of such medical events include allergic bronchospasm requiring intensive treatment in an emergency room or at home, blood dyscrasias or convulsions that do not result in inpatient hospitalization, or the development of drug dependency or drug abuse.

NOTE: A distinction should be drawn between serious and severe events. A severe event is a major experience of its type. A severe event does not necessarily need to be serious. For example, nausea, which persists for several hours, may be considered severe nausea but not a serious adverse event. On the other hand, a stroke that results in only a limited degree of disability may be considered a mild stroke but would be a serious adverse event.

Life-threatening Event: An adverse event is considered “life-threatening” if, in the view of either the investigator or sponsor, its occurrence places the patient or subject at immediate risk of death. It does not include an adverse event that, had it occurred in a more severe form, might have caused death.

Potential immune-mediated medical conditions (PIMMCs): FDA requires monitoring for specified known or suspected autoimmune disorders when testing novel adjuvants. PIMMCs will be recorded on the AE form and reported to IDRI Pharmacovigilance regardless of their attributed relationship to study injections. PIMMCs consist of any of the diagnoses listed in [Appendix 6](#) reported in study injection recipients at any time during the study period or after completion of the study.

All adverse events (including PIMMCs) will be reported on the Adverse Event eCRF using a recognized medical term or diagnosis that accurately reflects the event. Adverse event evaluations will be reviewed by the PI or by a designated medically qualified practitioner. Adverse event eCRF pages are to be completed by members of the study team designated in writing by the PI. The onset and resolution dates of the event and action taken in response to the event will be documented. All adverse events must be followed until resolution or stabilization is demonstrated. The resolution date will be recorded on the eCRF as the last date on which the participant experienced the adverse event. If the subject cannot recall the date of resolution, then the resolution date will be the visit date on which the study staff determines the AE to be resolved.

Adverse events that are still present at the end of the trial should be recorded as ongoing and be followed until resolved or considered stable. Information recorded on the eCRF must be substantiated in the source documents. If an adverse event evolves into a condition that becomes “serious,” it will be designated as serious on the Adverse Event eCRF and an SAE Report will be completed.

9.2.2 Assessment of Severity (Grading)

The safety concepts of “severity” and “seriousness” are distinct concepts. Severity refers to a degree of clinical manifestation. “Seriousness” refers to defined outcomes from an adverse event. A severe adverse event is not always serious and a serious adverse event is not always severe.

For all adverse events, the investigator is responsible for assessing the severity of the event and the causal relationship of the event to the study injection.

The severity of all adverse events, including clinical findings and abnormal laboratory values, will be classified as one of the following grades:

- Grade 1: Mild
- Grade 2: Moderate
- Grade 3: Severe

Toxicity tables are provided in the protocol appendices for the assessment of severity of specified adverse events. The toxicity table adverse event grades do not correlate directly with the classical severity grades of mild, moderate, and severe. For the purposes of recording events on the eCRF, Grade 1 events will be considered mild in severity, Grade 2 events will be considered moderate in severity, and Grade 3 events will be considered as severe. In the grading scale for local reactions ([Appendix 4](#)), certain local reactions such as erythema and induration are graded according to size. Laboratory values are graded according to level of deviation from the normal range.

For adverse events not listed in the toxicity tables, determination of severity requires some level of interpretation as outlined below. The degree of incapacity caused by the adverse event and the level of medical intervention required for treatment may be helpful in assessing the overall severity of the adverse event.

For example:

- “Mild” events are generally regarded as noticeable but have no impact on normal activities; they may or may not require over-the-counter treatment managed by the participant.
- “Moderate” events generally have some impact on an individual’s normal daily activities and may require general symptomatic medical intervention by a healthcare professional or by the participant.
- “Severe” adverse events may be incapacitating, leading to suspension of normal daily activities, and would generally require more immediate medical evaluation and intervention by a healthcare professional.

A change in severity of an adverse event will not be recorded as a new adverse event. Only the highest severity level that occurs during the entire period of the adverse event will be recorded on the eCRF with the onset and resolution dates encompassing the entire duration of the event.

9.2.3 Assessment of Causality (Relatedness to Study Injection)

For all adverse events, the investigator will determine a causal relationship to the study injection. A number of factors will be considered in making this assessment, including: 1) the temporal relationship of the event to the administration of the study injection, 2) whether an alternative etiology has been identified including the toxicity profile of any concomitant medication, and 3) biological plausibility.

The investigator will use the following guidelines to assess the causal relationship of an adverse event to study injection:

- **Not Related** to study injection (i.e., there is not a reasonable possibility that the administration of the study product caused the adverse event).
- **Possibly Related** to study injection (i.e., there is a reasonable possibility that the adverse event was caused by study injection. There must be a plausible mechanism for the event

to be related to study injection. The evidence is inadequate to accept or reject, or favors rejection of, a causal relationship; an association exists between the event and the study injection but there may also be an alternative etiology, such as characteristics of the participant's clinical status or underlying condition).

- **Probably Related** to study injection (i.e., it is likely that the adverse event was caused by administration of the study injection. The evidence favors acceptance of a causal relationship; an association exists between the event and receipt of the study injection and there is a plausible mechanism for the event to be related to the study injection, and an alternative etiology is not apparent).
- **Definitely Related** to study injection (i.e., the study injection is known to be the cause of the adverse event. The evidence establishes a causal relationship; an association exists between the event and receipt of the study injection and there is a plausible mechanism for the event to be related to the study injection, and causes other than the study injection have been ruled out).

For reporting purposes, consistent with NIAID guidelines, definitely, probably, and possibly related adverse events are considered **related** to study injection. Not related adverse events are considered **unrelated**.

For adverse events requiring immediate reporting, the PI and the Sponsor Medical Monitor both determine causality. It is expected that communication and consultation may occur in the assessment of the causality of adverse events. The greatest degree of causal relationship (definite > probable > possible > not related) determined by either the investigator or Medical Monitor after their discussions will determine the ultimate classification of the adverse event. Adverse events where the causality is not assessable will be considered related to the study injection.

Every effort should be made by the investigator to determine the existence of any pre-existing conditions that must be taken into consideration when assessing causal relationship of an adverse event. Pre-existing conditions should be recorded in the eCRF as baseline history and substantiated by appropriate source documentation. Intermittent conditions such as headaches in adults may not be present on Study Day 0 but may represent an adverse event if the frequency, intensity, or duration of the event is worse than usual following study injection.

9.2.4 Evaluation of Expectedness

Expected adverse events are adverse events consistent with the applicable product information provided by the sponsor (the Investigator's Brochure for an investigational product). The sponsor, in the person of the Sponsor Medical Monitor, determines expectedness. If the assessment is that the adverse event is expected, no further action is required. If the Sponsor Medical Monitor's assessment is that the adverse event is unexpected, then the event may represent a suspected unexpected serious adverse reaction (SUSAR) or expedited SAE.

9.2.5 Reactogenicity

Local site of injection reactions (pain, erythema, and induration) will be graded according to [Appendix 4](#). Specific solicited systemic reactions (headache, arthralgia, chills, loss of appetite, fever, fatigue, and myalgia) will be graded according to [Appendix 5](#).

9.2.6 Memory Aids

Memory aid booklets will be distributed to each subject to collect local and systemic adverse event information covering the 7-day period following the first and second study injections. All subjects will be instructed to record local and general signs and symptoms on individual memory aids on the evening of the day of injection and at approximately the same time daily for each of the six days following injection. Erythema and induration at the injection site will be measured in centimeters, using the measuring tool provided for that purpose. Subjects will also be asked to record any medications taken. The memory aid will be brought to the clinic on the scheduled visit 7 days after each injection for review and will be collected by the study research staff on Days 7 and 63. The memory aid is a tool to help aid the PI and/or designee to engage in a conversation with the subject about any AEs that may have occurred between visits. Memory aids not brought to the scheduled visit should be obtained before complete adverse event assessment can be performed and events discussed with the PI and/or designee. Adverse events obtained from the memory aid, as determined by the PI or designee, will not be directly recorded onto eCRFs. Any entry recorded by the subject on the memory aid that differs from the opinion of the investigator's evaluation of the event (e.g., the severity level of an event is changed after interviewing the subject) must be explained by notation in source documentation.

Subject-assessed symptoms related to the injection site in the memory aid will include injection site pain, redness (erythema), and hardening/swelling (induration).

Grading of **local pain** at the injection site will be according to the following definitions:

- None
- Mild (does not interfere with normal* daily activities)
- Moderate (repeated use of non-narcotic pain reliever > 24 hours or interferes with normal* daily activities)
- Severe (any use of narcotic pain reliever or prevents normal* daily activities)

Grading of **redness** and **hardening/swelling** at the injection site will be made according to the following (note: measurements are at the widest diameter):

- None (0 to < 2.5 cm in diameter)
- Mild (2.5 to 5 cm in diameter)
- Moderate (5.1 to 10 cm in diameter)
- Severe (>10 cm in diameter or necrosis or exfoliative dermatitis for redness)
(>10 cm in diameter or necrosis for induration)

Oral temperature will be measured daily and recorded in the memory aid. General signs and symptoms will be limited to headache, joint pain (arthralgia), chills, anorexia (loss of appetite), fever, tiredness (fatigue), and generalized muscle pain (myalgia). Grading of none, mild, moderate, and severe will be used according to the following definitions:

- None
- Mild (no interference with daily activity)
- Moderate (some interference with daily activity)
- Severe (Significant interference, prevents daily activity)

'Normal' daily activities include those performed by most able people, such as dressing, bathing, walking, driving, housekeeping; they do not include unusually strenuous activities that may be 'normal' for certain individuals such as lifting heavy weights.

During the 60-minute observation period following the first study injection, subjects will be trained by the research staff on the proper completion of the memory aid and the schedule for completion. Subjects will also be trained in the proper procedure for taking oral temperature and will be asked to record their oral temperature each evening in the memory aid. Digital oral thermometers will be provided to all subjects for oral temperature readings. Subjects will also be provided with a measuring tool and trained on how to measure local redness (erythema) and hardening/swelling (induration).

Explicit choices for mild, moderate, and severe reactions will be indicated in the memory aid by the subjects, as defined above.

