3.2 Study Outcome Measures

3.2.1 Primary Outcome Measures

- The number of subjects experiencing solicited local injection site reactions within 7 days following each study injection.
- The number of subjects experiencing solicited systemic reactions within 7 days following each study injection.
- The number of subjects spontaneously reporting adverse events from Day 0 through Day 84.
- The number of serious adverse events considered related to any of the study injections reported at any point during the study period.

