7.2 Day 0 Enrollment/Baseline Evaluations and First Study Injection

Prior to Study Injection:

- Review Inclusion/Exclusion criteria as specified for the initial study injection.
- Review concomitant medications.
- Obtain vital signs (BP, P, RR, oral temperature).
- Perform a targeted physical exam if indicated based on symptoms.
- Perform urine pregnancy test for females of childbearing potential within 24 hours prior to study injection. Test results must be confirmed as negative prior to study injection.
- Review of acceptable contraceptive methods (female subjects only).
- Counseling on avoidance of pregnancy (for all female subjects of childbearing potential).
- Collect nasal swab
- Collect tears
- Collect blood prior to study injection for baseline immunologic evaluations for:
 - Serum for IgG ELISA
 - Serum to bank (baseline for auto-immune testing, if indicated)
 - Whole blood for MGIA
 - PBMC isolation

- Perform randomization procedures.

Study Injection:

- Administer study injection in the non-dominant deltoid unless there is a reason to inject in the alternate deltoid. Both injections are preferably administered in the same arm.
- Dispense memory aid, measuring tool, and thermometer.

Immediately Following Study Injection:

All subjects will be observed for a minimum of 60 minutes following study injection. After 60 minutes:

- Obtain vital signs (BP, P, RR, oral temperature).
- Examine the injection site and assess any AE/SAEs (including specific solicited systemic reactions: headache, arthralgia, chills, loss of appetite, fever, fatigue, and myalgia), prior to discharge from the clinic.
- Request subject to bring their completed memory aid to the next clinic visit.

All subjects will be asked to record, on a subject memory aid, daily maximum temperatures, symptoms for 7 days, measure erythema or induration if any, beginning with the day of study injection and report them to the clinic staff. Subjects will be asked to bring their completed memory aid to the Day 7 post-injection clinic visit.

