9.6.2 Rules for Suspension of the Entire Study

The study will be immediately suspended (paused) and no additional study injections administered, pending review and discussion of all appropriate safety data by the SMC, if one or more subjects in any treatment group experience any of the following adverse events:

- Anaphylaxis or bronchospasm within 4 hours of study injection indicative of an immediate hypersensitivity reaction to the vaccine and not attributable to another cause.
- Any systemic rash, including but not limited to urticaria, generalized petechiae, or erythema multiforme, not attributable to another cause.
- Tissue necrosis at the study injection site.
- Any other serious adverse event deemed to be possibly, probably, or definitely relatable to the study injection by the PI or Sponsor Medical Monitor, based on close temporal relationship or other factors.

The study will also be immediately suspended (paused) and no additional study injections administered pending review and discussion of all appropriate safety data by the SMC if three or more subjects experience the following AEs determined to be related to study injection:

- Changes in laboratory parameters that meet Grade 3 severity.
- High fever (oral temperature $\geq 102.2^{\circ}\text{F}/39^{\circ}\text{C}$) within 1 week following study injection associated with constitutional symptoms and not attributable to another cause.
- Severe injection site reactogenicity that involves Grade 3 local pain, induration, or erythema.

Study suspension or termination will only apply to additional study injections. Subjects for whom their study injections are discontinued will remain in limited visit follow-up for safety evaluations and immunology blood draws.

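### The protocol asks for a daily maximum temperature but trains subjects to record an evening one, so a fever peaking at another hour can be missed or under-graded in both groups

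*Protocol*

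**What the plan says.** Protocol Section 7.2 sets out what is entered after the first injection: "All subjects will be asked to record, on a subject memory aid, daily maximum temperatures, symptoms for 7 days". Section 7.5 repeats this for the second injection.

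Protocol Section 9.2.6 describes the memory aid and the training. Signs and symptoms are entered "on the evening of the day of injection and at approximately the same time daily for each of the six days following injection". On temperature it says "Oral temperature will be measured daily and recorded in the memory aid", and that subjects "will be asked to record their oral temperature each evening in the memory aid". It does not mention a maximum temperature.

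The temperature record is used in three places:

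- **Primary outcome (Protocol Section 3.2.1):** "The number of subjects experiencing solicited systemic reactions within 7 days following each study injection". Fever is one of seven solicited systemic reactions.
- **Grading and summaries:** Protocol Section 9.2.5 sends these reactions to Appendix 5, which grades fever by oral temperature: 38.0 to 38.4 °C is Grade 1, 38.5 to 38.9 °C is Grade 2, and 39.0 °C or more is Grade 3. SAP Section 7.2.2.3 summarises each individual reaction and its maximum grade in each 7-day period.
- **Halting rules (Protocol Sections 9.6.1 and 9.6.2):** an oral temperature of at least 39 °C "within 1 week following study injection associated with constitutional symptoms and not attributable to another cause" stops further injections in that subject. If it is judged related and occurs in three or more subjects, it pauses the study.

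**The concern.** One reading at a fixed hour is not a daily maximum. A subject who follows the Section 9.2.6 training literally does not produce the value that Sections 7.2 and 7.5 ask for, and nothing in the protocol closes the gap.

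Fever is more exposed to this than the other six solicited systemic reactions. They are graded by their effect on activity, so an interview can recover a headache or chills that went unrecorded. It cannot recover a peak temperature that nobody measured. Section 2.3.1 lists fever among the possible systemic reactions to GLA-SE, so it is a relevant tolerability signal here. Section 6.5 asks subjects to avoid antipyretics for only the first 24 hours, and later use could lower an evening reading further.

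At stake are the fever rate, its severity distribution, and whether a high fever leaves the measurement on which the 39 °C criterion depends.

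**Working it through.** The plan states no figure on this point, so there is none to reproduce. The check is a comparison of texts, followed by illustrations on stated assumptions.

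**1. The instructions side by side**

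| Question | Protocol 7.2 and 7.5 | Protocol 9.2.6 |
|---|---|---|
| Which temperature? | The day's maximum | Oral temperature, no maximum mentioned |
| When? | Not stated | Each evening |
| How many readings? | Not stated | Daily, no count |
| A reading when feeling feverish? | Not stated | Not stated |

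The evening of injection plus six further days gives 1 + 6 = 7 scheduled entries per injection. Other temperatures come from the clinic 60 minutes after injection (7.2, 7.5), from the Day 7 and Day 63 visits (7.3, 7.6), and from unscheduled visits where vital signs are clinically indicated (7.12).

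**2. Effect on grade**

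Grade 1 starts at 38.0 °C and Grade 3 at 39.0 °C, so the whole scale spans 39.0 − 38.0 = 1.0 °C. A fever that peaks at 39.0 °C and reads 38.4 °C in the evening (0.6 °C lower) is recorded as Grade 1. If it reads 37.9 °C (1.1 °C lower), no fever is recorded.

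**3. Chance that one reading a day catches a fever**

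Assumptions: one reading per 24 hours, a single episode above threshold for d hours, and onset at random relative to the reading. The documents do not give d. Capture probability = d/24 for d up to 24.

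- 6 hours: 6/24 = 25%
- 12 hours: 12/24 = 50%
- 18 hours: 18/24 = 75%

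**4. Effect on the three-subject pause**

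Assumptions: 48 subjects, high fever considered alone, and every case related and accompanied by constitutional symptoms. The true rate p and the capture proportion s are both assumed. The number detected is binomial with n = 48 and probability p × s, and the table gives P(3 or more).

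| True high-fever rate p | s = 100% | s = 90% | s = 75% | s = 50% |
|---|---|---|---|---|
| 2% | 0.07 | 0.06 | 0.04 | 0.01 |
| 5% | 0.43 | 0.37 | 0.27 | 0.12 |
| 10% | 0.87 | 0.82 | 0.71 | 0.43 |

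At p = 5% the expected number detected falls from 48 × 0.05 = 2.4 to 48 × 0.05 × 0.5 = 1.2 when half are captured. The direction follows whenever capture is incomplete. The size depends entirely on p and s.

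**5. Effect on the primary count**

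The outcome counts subjects with any of the seven reactions. A missed fever removes a subject from the count only if that subject has none of headache, arthralgia, chills, loss of appetite, fatigue or myalgia in the period. The fever row and the fever severity distribution have no such protection.

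**The case against.** The texts can be read together: Sections 7.2 and 7.5 say what is entered, and Section 9.2.6 says when. On that reading the subject enters the day's highest temperature each evening. Section 9.2.6 nowhere says that only one reading is taken, and neither the memory aid form nor the Study Specific Procedures Manual is among the documents. This stands as far as it goes, so evening-only measurement is an inference. It does not remove the problem, because no section asks for the extra readings from which a maximum could be found.

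There are other routes to a fever. Besides the clinic temperatures, fever is itself a listed symptom on the memory aid, and the aid prompts an investigator interview rather than feeding the eCRF directly. This also stands: a fever can be missed, not will be. An Appendix 5 grade and the 39 °C criterion still need a measured value.

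The halting criterion also requires constitutional symptoms, so a high fever without them would not have counted in any case. A reader might infer that fever is the only systemic event that can pause the study. Section 9.6.2 does not support that: anaphylaxis or bronchospasm, systemic rash, and any related serious event each pause it in a single subject. Fever is only the one solicited systemic reaction named there.

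The percentages in the working rest on no input from the documents. Onset after a known injection time is not random, and a fever lasting several days has several chances of being caught. They are illustrations.

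**Conclusion.** The inconsistency is real and minor. The protocol asks for a daily maximum, trains subjects to make an evening record, and gives no instruction that turns one into the other. If only an evening reading is taken, fevers peaking at other hours can be missed or under-graded. This mainly affects the fever-specific and maximum-severity summaries and the measured 39 °C criterion; the any-reaction primary count is largely shielded.

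Two stronger conclusions are tempting. One is that fevers were in fact missed, at some stated rate. The documents show neither what the memory aid said nor how many readings subjects took, so the size cannot be determined. The other is that the comparison of presentations is biased. Both groups have the same procedure at one site with blinded assessors (Section 5.4.2), so the likely effect is under-ascertainment in both groups, not an advantage to either.

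**What to change.** Reconcile Protocol Sections 7.2, 7.5 and 9.2.6 and the memory aid to one instruction that yields a daily maximum: take the scheduled evening reading, take another whenever the subject feels feverish, and record the highest value of the day. Grading by Appendix 5 needs no change.

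The cost is wording on the memory aid and in training, since Section 9.2.6 already supplies thermometers to all subjects. The downside is that symptom-prompted readings are less standardised than a fixed-time one, and fever incidence may look slightly higher.

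SAP Section 1 says that the safety analysis has already been performed, so for this trial only the reporting can change. The study report should state which instruction the memory aid carried and, if evening readings were the practice, label the fever rates as such. That costs a sentence and a table footnote.
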